#### 3.1.4 Safety Monitoring

A Data Safety Monitoring Board will not be used for this study given that it is a small scale, single center study. However, safety including SAEs will be monitored by study staff in an ongoing fashion during patient study participation.

#### 3.2 Study Population

The study population includes recipients of renal allografts in the first three months after first episode of transplantation that demonstrate side effects from the standard calcineurin inhibitor based regimen. CNI toxicity is delineated as follows:

1. Neurologic toxicity, defined as tremor, altered mental status, or seizure

2. Renal toxicity, defined as GFR <60

3. Metabolic toxicity, defined as a new requirement for medication to control hyperglycemia

4. Hematologic toxicity, defined as development of thrombotic microangiopathy History of induction therapy with either basiliximab or antithymocyte globulin is permissible for study entry; as our center primarily uses basiliximab this will be the predominant induction therapy for study participants.

#### 3.3 Criteria for Evaluation

Primary Measures:

- Donor specific antibody testing at Month 6
- Cell surface cytokine secretion in response to donor cell antigen by direct and indirect stimulation at Month 6
- Cell surface cytokine secretion in response to CMV and EBV antigens by direct and indirect stimulation at Month 6
- Immunophenotyping to determine overall immune profile at Month 6
- Patient and functional graft survival in stable renal transplant recipients

Secondary Outcome Measures:

- Donor specific antibody testing at Months 1 and 3
- Cell surface cytokine secretion in response to donor cell antigen by direct and indirect stimulation at Months 1 and 3 (and month 12 if continuing in study)
- Cell surface cytokine secretion in response to CMV and EBV antigens by direct and indirect stimulation at Months 1 and 3 (and month 12 if continuing in study)

#### Definitions

Acute and chronic rejection will be defined using the Banff 97 working classification of kidney transplant pathology.[8] Standard clinical and histologic criteria for calcineurin inhibitor associated nephrotoxicity will be used.[9] Full Banff criteria analysis will be provided for each biopsy performed.

#### 3.4 Sample Size Determination

Because of the exploratory nature of this analysis, it is not possible to estimate power for this study, a goal of 20 patients was used similar to other immunologic pilot studies and is a reasonable goal for rapid accrual at our center.

#### 3.5 Interim Analyses

No interim analyses will be performed. However, safety and any SAEs will be monitored on a continuous basis.

#### 4 STATISTICAL METHODOLOGY 4.1 Data Set Descriptions

Data sets will be generated for all patients enrolled in the study with recorded frequency of alloantigen specific cells at weeks 0, 4, 12, and 24 after study start after both direct and indirect stimulus, frequency of anti CMV and anti EBV specific cells at weeks 0, 4, 12, and 24, and frequency of cell populations as determined by immunophenotyping analysis at weeks 0, 4, 12, and 24. A representative group of 20 control patients receiving standard immunosuppressive medications will be identified from an ongoing observational study at our center using matching criteria described above. Patient matching will be performed in a blinded fashion. The ongoing observational study at UCLA is led by [name] and all patients undergoing kidney transplantation at UCLA are eligible for enrollment for an ongoing evaluation of immunologic predictors of rejection. PBMCs have been aliquoted and stored from these patients at time points post transplantation similar to those described in this protocol so they will be an ideal source for comparative analysis.

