Mechanisms of belatacept effect on alloimmunity and antiviral response after kidney transplantation

An Investigator-Initiated Research Proposal Concept # 56950 BMS study # IM 103-309

[name]. Principal Investigator UCLA Division of Kidney Transplantation [name] [contact]

[name]. Co-investigator Director of the UCLA Immunogenetics Center Department of Pathology and Laboratory Medicine [name]

[name]., Ph.D. Co-investigator UCLA Division of Infectious Diseases [name]

SYNOPSIS

Title of Study: Mechanisms of belatacept effect on alloimmunity and antiviral response after kidney transplantation

Estimated Number of Study Centers and Countries/Regions: 1

Study Phase: 4

Research Hypothesis: Switching to a belatacept-based immunosuppression regimen after kidney transplant will have a significant impact on antibody and T cell-mediated immune response as compared with control patients as measured in peripheral blood at 6 months after belatacept switch and comparable safety and efficacy as compared with calcineurin inhibitor (CNI) based regimens.

Primary Objective: To analyze the effect of switching from CNI to belatacept in patients with evidence of CNI toxicity on the development and maintenance of immune memory in response to both alloantigen and viral antigens commonly encountered after transplant, and to assess the safety and efficacy of conversion to belatacept as maintenance immunosuppression in combination with prednisone and mycophenolate mofetil.

Study Design: Open label, single center clinical trial. Patients with evidence of CNI toxicity will be eligible for switch to belatacept-based regimen within the first three months after transplant. All enrolled subjects will also receive concomitant maintenance immunosuppression with mycophenolate mofetil and corticosteroids.

Duration of Study: 6 months, with option to extend to 12 months of belatacept treatment Number of Subjects: 20 Study Population: Kidney transplant recipients within the first three months of their first transplant with evidence of CNI toxicity.

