#### 3.1.2 Overview

This is an open label, single center clinical trial. All subjects will have undergone kidney transplantation with induction immunosuppression and will be on maintenance therapy with a CNI (tacrolimus or cyclosporine) plus mycophenolate mofetil and corticosteroid maintenance therapy at the time of enrollment. 20 subjects with evidence of CNI toxicity (see definition below) in the first three months after transplant will be enrolled to switch to the belatacept regimen. These enrolled subjects will be compared with 20 matched patients from an ongoing observational study of kidney transplant patients at our center.

All subjects will also receive induction with basiliximab and a background maintenance immunosuppressive regimen of MMF and corticosteroids.

Study patients will receive intravenous belatacept at 5mg/kg every two weeks at day 1 and weeks 2, 4, 6, and 8, and then monthly at months 3, 4, and 5. At month 6 patients may elect to continue for an additional six-month period of belatacept administration

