#### 3.1.3 Primary Outcome Measures and Justification

Patients switched to the belatacept-based regimen will be compared to a group of matched patients on standard CNI-based immunosuppression regimen on the following primary outcome measures: (1) the donor specific antibody level, (2) the frequency of alloantigen and viral antigen reactive cells as measured by cell surface cytokine analysis, and (3) the frequency of immunophenotypes described below at Month 6. Matching will be performed based on age within 10 years, sex, deceased versus living transplant, and DSA level at time of enrollment.

The intent is to investigate differences in these measures as a means to determine the immunologic mechanism of action of belatacept. These endpoints were selected based on previous research showing that these measures are key determinants of immune function in transplant patients. In addition, baseline levels at time of enrollment of these endpoints will be compared with results from months 1, 3, and 6, as well as month 12 if patients elect to continue for an additional 6 months of belatacept therapy. Month 6 will be used as the primary measure of outcome for the immunologic assays, with months 1, 3 and 12 if applicable as the secondary measures.

To perform these mechanistic studies, blood from subjects will be collected at each study time point as described below and peripheral blood mononuclear cells (PBMCs) will be isolated and frozen for future analysis.

For analysis of response to alloantigen stimulation, PBMCs will be incubated with either intact donor cells or membrane preparations from donor cells to test either direct or indirect immunity, respectively. Following incubation, a cocktail of fluorescent-conjugated monoclonal antibodies will be added to detect relevant immunologic subclasses of cells as well as relevant surface cytokines and the percentage of each lymphocyte subset will be analyzed using flow cytometry according to previously published protocols developed at the UCLA Immunogenetics Center [7].

For analysis of response to viral antigens, PBMCs will be extracted and stored as described above using well-characterized CMV or EBV antigens for stimulation during the incubation period using a similar protocol adapted for detection of relevant antiviral immune lymphocytes.

Overall immune profile will also be analyzed by immunophenotyping using multiparameter flow cytometry using the panels described below:

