5.2 Exclusion Criteria Gender and Reproductive Status

1) WOCBP who are unwilling or unable to use an acceptable method to avoid pregnancy for the entire study period and for up to 8 weeks after the last infusion.

2) Women who are pregnant or breastfeeding

3) Women with a positive pregnancy test on enrollment or prior to study drug administration

4) Males unwilling or unable to use an adequate method of contraception for the entire study period and for up to 8 weeks after the last infusion of study medication

Immunologic status

5) Subjects with PRA  $\ge$  30% at time of transplant

6) Subjects with zero HLA antigen mismatched donors (either from related or unrelated donor)

7) Subjects with any prior solid organ transplant (including kidney)

8) Subjects receiving a concurrent solid organ (heart, liver, pancreas) or cell (islet, bone marrow, stem cell) transplant

9) Subjects with a history of biopsy-proven acute rejection post-transplant (humoral or cellular) in the first three months post transplantation

Infection related risks

10) Subjects who are hepatitis C antibody-positive or polymerase chain reaction

(PCR)-positive for hepatitis C

11) Subjects who are hepatitis B surface antigen-positive or PCR-positive for hepatitis B

12) Subjects with known human immunodeficiency virus (HIV) infection

13) Subjects with active tuberculosis (TB) requiring treatment within the previous 3 years or any subject who previously required triple (or more) combination therapy for TB.

14) Subjects who are EBV antibody negative and have received grafts from EBV antibody positive donors.

Prohibited Therapies and/or Medications

15) Subjects who have used any investigational drug within 30 days prior to the Day 1 visit

16) Subjects previously treated with belatacept

18) Use of mTOR inhibitors at any time after transplantation

Other Exclusion Criteria

18) Prisoners or subjects who are compulsorily detained (involuntarily incarcerated) for treatment of either a psychiatric or physical (e.g., infectious disease) illness must not be enrolled into this study.

19) Subjects who have difficult i.v. access or other reasons that would likely preclude medication administration

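### Controls need not have CNI toxicity or meet the trial's exclusion criteria, so the month-6 comparison can mix the belatacept effect with how the two groups were selected

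*Combined protocol and SAP*

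**What the plan says.** The primary objective in the synopsis begins: "To analyze the effect of switching from CNI to belatacept in patients with evidence of CNI toxicity". Section 3.1.2 follows it: "20 subjects with evidence of CNI toxicity (see definition below) in the first three months after transplant will be enrolled to switch to the belatacept"-based treatment. Sections 3.2 and 5.1 define toxicity as neurologic, renal (GFR <60), metabolic or hematologic. Section 5.2 then excludes, among others, patients with PRA of 30% or more, a zero-mismatch donor, any prior solid organ transplant, a concurrent organ or cell transplant, biopsy-proven acute rejection in the first three months, EBV-negative status with an EBV-positive donor, or mTOR inhibitor use.

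The control group is described separately. Section 4.1 says: "A representative group of 20 control patients receiving standard immunosuppressive medications will be identified from an ongoing observational study at our center". Of that study it says that "all patients undergoing kidney transplantation at UCLA are eligible for enrollment for an ongoing evaluation of immunologic predictors of rejection". Under section 3.1.3 the switched patients are "compared to a group of matched patients on standard CNI-based immunosuppression regimen", and "Matching will be performed based on age within 10 years, sex, deceased versus living transplant, and DSA level at time of enrollment". Section 4.1 adds that matching is done blind.

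Section 4.2 makes the primary immunologic comparison a Mann-Whitney U test at 24 weeks against controls at a comparable time point. It adds a baseline-to-week-24 comparison in patients and a repeated-measures ANOVA against controls. No covariates are named for any of these.

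**The concern.** The question is what switching does in patients who already have CNI toxicity. The natural comparator is a similar patient with toxicity who stayed on CNI. The plan does not ask for that patient. A control chosen exactly as sections 3.1.3 and 4.1 direct may have had no toxicity. The same control may also be someone section 5.2 would have kept out of the belatacept group.

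Several of these differences bear directly on the endpoints:

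- A control with a zero-mismatch donor offers little or no HLA target for donor-specific antibody or for the alloantigen assays.
- A sensitized or repeat recipient may bring more alloimmune memory.
- An EBV-negative recipient of an EBV-positive graft can enter the control group, while the response to EBV antigens is a primary endpoint.
- Early rejection is screened out of one group only, while section 1.1 hypothesizes similar rejection rates in the two.

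Section 3.1.3 says the differences are meant to reveal how belatacept acts, and section 1.1 states directional hypotheses against controls. A month-6 difference that partly reflects who was selected would be read as mechanism.

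**Working it through.** **Step 1: set the requirements side by side.**

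| Feature | Belatacept subject | Control |
|---|---|---|
| CNI toxicity within 3 months | Required (3.2, 5.1) | Not required |
| PRA below 30% | Required (5.2) | Not required |
| At least one HLA mismatch | Required (5.2) | Not required |
| First, single-organ transplant | Required (5.1, 5.2) | Not stated |
| No early biopsy-proven rejection | Required (5.2) | Not required |
| Not EBV-negative with EBV-positive donor | Required (5.2) | Not required |
| No mTOR inhibitor after transplant | Required (5.2) | Not stated beyond a standard CNI-based regimen |
| Age, sex, donor type, enrollment DSA | Basis of matching | Matched (3.1.3) |

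The opening line of section 5 does not close the gap. It governs entry into this study, and section 3.1.2 distinguishes the enrolled subjects from the observational-study patients they are compared with.

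**Step 2: size of the risk for the immunologic endpoints.** The plan states no alpha, effect size or SD, so there is no figure of its own to reproduce. Assumptions: no drug effect, 20 against 20, normal outcomes with SD 1, two-sided Mann-Whitney at 5%, 20,000 simulated trials.

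- All controls differ by a uniform shift (a stand-in for the toxicity difference): 0 / 0.2 / 0.3 / 0.5 SD gives rejection in about 5% / 9% / 15% / 32% of trials.
- Only some controls carry a trait worth 1 SD (a stand-in for sensitization or zero mismatch): a share of 10% / 25% / 50% gives about 5.7% / 10.7% / 29%.
- Traits in opposite directions partly cancel: 10% of controls at +1 SD with 10% at −1 SD gives 5.0%, and 25% with 10% gives 6.7%.

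For scale, the shift detectable with 80% power at 20 per group is (1.96 + 0.84) × √(2/20) = 0.89 SD, or 0.89/√0.955 = 0.91 SD for Mann-Whitney. A shift of 0.3 to 0.5 SD is not small beside that.

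**Step 3: rejection.** Section 7.3.6 gives about 10% acute rejection in the first year on a cyclosporine-based regimen. Let e = 0.10 × (share of those rejections that occur before enrollment). A patient selected as rejection-free then has a later rate of (0.10 − e)/(1 − e).

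- Share 25%: (0.10 − 0.025)/(1 − 0.025) = 7.7%
- Share 50%: (0.10 − 0.05)/(1 − 0.05) = 5.3%
- Share 75%: (0.10 − 0.075)/(1 − 0.075) = 2.7%

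Unrestricted controls stay at 10%. The shares are assumptions, and the gap is smaller for subjects who enroll soon after transplant.

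**The case against.** The strongest reply has four parts.

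- DSA at enrollment is a matching variable, so the DSA endpoint has some protection. This stands: the concern is weakest there. But candidates with no DSA at enrollment look alike on that variable whatever their PRA, mismatch or EBV status.
- The baseline-to-week-24 comparison and the repeated-measures ANOVA can reduce stable baseline differences. This stands in part. Neither is the primary comparison, and the within-patient comparison has no control. Neither deals with trajectories that diverge because of the toxicity itself.
- Matching is blinded. That limits choosing controls by outcome; it does not make the two populations alike.
- The study is exploratory, with 20 subjects and no power claim. This explains the missing power calculation and tempers the seriousness. It does not excuse a selection gap that is cheap to narrow when the hypotheses are comparative.

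A reader might infer more than the documents allow. They do not show that controls will be mostly free of toxicity: GFR <60 is a broad criterion, and many controls may meet it. They do not show which way the bias runs, since sensitized controls would favor the lower-DSA hypothesis and zero-mismatch controls would work against it. Nor do they support a large false-positive rate as an estimate. A uniform 0.8 SD shift would give about 67%, but nothing in the documents points to a shift of that size.

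**Conclusion.** The concern holds in a limited form. Followed as written, the plan permits controls without CNI toxicity and controls who would fail section 5.2, and compares them with belatacept subjects without adjustment. The month-6 contrast can therefore mix the drug effect with the reason for switching and with PRA, HLA mismatch, prior or concurrent transplant, early rejection and EBV serostatus.

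Size and direction are unknown. Under the stated assumptions the false-positive rate is about 6% to 11% when 10% to 25% of controls carry a 1 SD trait, and 15% to 32% for a uniform shift of 0.3 to 0.5 SD. These figures illustrate sensitivity; they do not predict the bias in this trial. Because the groups are not randomized, even well-restricted controls would not by themselves establish that a difference is due to belatacept.

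**What to change.** Amend sections 3.1.3 and 4.1 so that the following applies before the stated matching:

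1. **Restrict the pool.** Controls meet the same section 5.2 criteria as belatacept subjects, judged at the index date. These include first and kidney-only transplant, PRA below 30%, at least one HLA mismatch, no early biopsy-proven acute rejection, not EBV-negative with an EBV-positive donor, and no mTOR inhibitor use.
2. **Define the index date.** Place it at the same time since transplant as the matched subject's Day 1, with the control on CNI at that date and no selection on anything that happens later. This also gives meaning to enrollment DSA and to the comparable time point in section 4.2, neither of which is defined for a control. The date on which toxicity appeared would not serve, because a belatacept subject's Day 1 may come weeks after it.
3. **Handle toxicity.** Prefer controls who met a section 3.2 criterion by the index date. Where the pool is too small, match at least on GFR at index, report toxicity status by group, and state that the between-group comparison is non-randomized and descriptive as to attribution to belatacept.

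The cost is protocol wording and a chart filter on an existing cohort with stored samples. The downside is a smaller control pool, so the 10-year age caliper may have to be loosened.

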Test Product, Dose and Mode of Administration, Duration of Treatment: Study patients will receive intravenous belatacept at 5mg/kg every two weeks at day 1 and weeks 2, 4, 6, and 8, and then monthly at months 3, 4, and 5. At month 6 patients may elect to continue for an additional six month period of belatacept administration. Peripheral blood mononuclear cells (PBMCs) and sera for antibody testing will be collected at time of study entry and at 4, 8, 12, and 24 weeks after belatacept start, frozen and banked at our center, and analyzed in batch fashion for development of humoral and cell mediated immunity. Patients who elect to receive an additional 6 months of belatacept treatment will undergo additional immunologic analysis at 1 year after study entry.

Reference Therapy, Dose and Mode of Administration, Duration of Treatment: Immunologic evaluations performed on study patients will be compared with a matched group of 20

control patients receiving conventional immunosuppressive therapy and participating in an ongoing observational trial regarding immunologic mechanisms contributing to rejection in kidney transplant patients.

Criteria for Evaluation:

Primary Outcome Measures:

- Donor specific antibody testing at Month 6
- Cell surface cytokine secretion in response to donor cell antigen by direct and indirect stimulation at Month 6
- Cell surface cytokine secretion in response to CMV and EBV antigens by direct and indirect stimulation at Month 6
- Immunophenotyping to determine overall immune profile at Month 6
- Patient and functional graft survival in stable renal transplant recipients

Secondary Outcome Measures:

- Donor specific antibody testing at Months 1 and 3 (and month 12 if continuing in study)
- Cell surface cytokine secretion in response to donor cell antigen by direct and indirect stimulation at Months 1 and 3 (and month 12 if continuing in study)
- Cell surface cytokine secretion in response to CMV and EBV antigens by direct and indirect stimulation at Months 1 and 3 (and month 12 if continuing in study)

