#### 1.2 Study Rationale

As belatacept comes into increasing clinical use, it is important to reach a better understanding of its immunologic mechanism of action. As the drug was engineered as a costimulation pathway inhibitor, we would hypothesize that its main effects would be on the activation of naïve T cells; however, an impact on pre-existing memory cells may also be seen. Both direct and indirect immunity play a role in allograft rejection after transplant, and it is important to differentiate between these two mechanisms as belatacept may affect each pathway differently: Direct recognition of alloantigen occurs when donor antigen presenting cells (APCs) present antigen to host T cell, as seen in early rejection, in contrast indirect recognition occurs when host APCs present either allo-antigen or viral antigen to host T cells.

It is known from Phase III trials that decreased formation of donor specific antibodies (DSA) are seen in patients treated de novo with belatacept compared with cyclosporine with both

standard and extended-criteria donors, [1,2] however, the mechanism behind this observation is unknown, and it is unclear whether this same affect might be anticipated in patients switched to belatacept one to three months post transplant. Finally, an increased frequency of post-transplant lymphoproliferative disorder in patients naïve for EBV with EBV positive donors (D+/R-) was also seen in these studies; this may reflect inhabitation of the development of antiviral immunity, but it is unclear how important the presence or lack of virus-specific memory T cells is in this response. Our laboratory is uniquely suited to perform a study of this nature given our experience and expertise in studies of immunity in transplant recipients as the designated investigative laboratory for the NIH-sponsored Clinical Trials in Organ Transplantation Study 2 (CTOT-2).

Figure 1: Model of belatacept action in alloimmunity and viral antigen recognition

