#### 4.2 Analyses

#### Immunologic mechanisms

Primary endpoints will be patient immune analysis at 24 weeks (end of study) as compared with control patients at a comparable time point for DSA, frequency of alloantigen and viral antigen reactive cells, and frequency of the immunophenotypes described above, comparison to be performed by Mann Whitney U test. In addition, a comparison will be made between patients' baseline and week 24 levels. ANOVA repeated measurement analysis will be used to evaluate immune measurements taken over time as compared with control patients

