#### 7.2.1 Screening/Baseline Evaluations

a) Screening may occur at any time for subjects 0 to 3 months after kidney transplantation who may meet study criteria

b) If patients appear to be possible candidates for enrollment, obtain written informed consent and enroll the subject. Consent must be obtained prior to any change in medical therapy or any procedure performed solely for the purpose of this study (A subject is considered enrolled in the study upon signing informed consent. Some standard-of-care

procedures routinely obtained for transplant subjects, regardless of study involvement, are likely to be obtained prior to study participation consent date, and should be documented as such.)

- c) Assign a unique study number to the patient
- d) Obtain complete medical history and physical examination.

e) Obtain body weight (clothes on, shoes off), and measure vital signs (blood pressure (BP), heart rate, temperature, and respiration).

f) Study labs will be drawn by obtaining whole blood and sending it via courier to the Immunogenetics Center for separation into PBMC and serum and storage. PCR testing will be performed.

g) DSA testing

h) Check and record all concomitant medications

7.2.2 Day 1

a) Confirm all inclusion/exclusion criteria.

b) Obtain height and body weight (clothes on, shoes off), and measure pre-dose vital signs (BP, heart rate, temperature and respiration). Height and weight recorded for Day 1 can be obtained 1 day prior, if necessary.

c) Assess and record AEs pretreatment.

d) Check and record any changes in concomitant medications.

e) Ensure all pretreatment (baseline) laboratory assessments and procedures have previously been obtained, or obtain at Day 1 prior to start of any study dosing (i.e., a negative serum pregnancy test must be confirmed within 72 hours of initiation of study dosing, if previous test is not within 72 hours, repeat prior to dosing at Day 1). Draw baseline whole blood for immunology analysis if not previously drawn

f) Administer study medication (belatacept 5 mg/kg over 30 minutes i.v. )

g) Continue daily dosing of prednisone, MMF, doses to be determined by the subject's treating physician, to continue throughout the duration of the study following practices of standard medical care

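### Controls have no stated eligibility rule or week 0, while rejection is counted from transplant, so only the belatacept group is sure to carry rejection-free time before the switch

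*Combined protocol and SAP*

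**What the plan says.** **Source of controls.** The synopsis (Reference Therapy) describes them as "control patients receiving conventional immunosuppressive therapy and participating in an ongoing observational trial". Section 4.1 adds that "all patients undergoing kidney transplantation at UCLA are eligible for enrollment for an ongoing evaluation of immunologic predictors of rejection".

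**Matching.** Section 3.1.3: "Matching will be performed based on age within 10 years, sex, deceased versus living transplant, and DSA level at time of enrollment". Time since transplant, freedom from rejection and CNI toxicity are not matching factors. Section 5 sets its criteria for entry into this study and does not mention the controls.

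**Entry of belatacept subjects.** Exclusion 9 in section 5.2 removes "Subjects with a history of biopsy-proven acute rejection post-transplant (humoral or cellular) in the first three months post transplantation". Section 7.2.1 states "Screening may occur at any time for subjects 0 to 3 months after kidney transplantation", whereas section 1.2 speaks of "patients switched to belatacept one to three months post transplant".

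**Time origin for clinical outcomes.** Section 2.1 lists survival and rejection at 12 months post transplant among the primary outcomes. Section 3.1.3 reads rejection and survival at 6 and 12 months post transplant. Section 4.2 summarises cumulative rejection without naming an origin. The hypothesis in section 1.1 is that the two groups have alike rejection rates, with no margin.

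**Timing of immune samples.** Section 4.1 says control cells were stored at "time points post transplantation similar to those described in this protocol". Section 4.2 makes the week 24 comparison "as compared with control patients at a comparable time point for DSA" and the other immune measures.

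**The concern.** To enter, a belatacept subject must have come through the weeks between transplant and switch alive and without biopsy-proven rejection. If follow-up is counted from transplant, those weeks add time at risk but cannot add a rejection. A control from an all-comers cohort can reject in the same weeks and be counted. This is immortal-time bias in the belatacept group's favour. It matters because the hoped-for finding is similarity, and this mechanism pulls a true post-switch excess towards parity.

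At the 6-month post-transplant reading, a subject who switched at 0-3 months has also had only 3-6 months since the first belatacept dose.

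Other one-sided criteria add to the imbalance. The PRA and prior-transplant exclusions may favour belatacept. The zero-mismatch exclusion may work against it. So may entry on CNI toxicity, possibly through more for-cause biopsies, since section 6.2.6.5 leaves biopsy to centre practice. The EBV exclusion bears on the PTLD summary.

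For the immune endpoints, the wording shows an intent to align the groups but fits two anchors: time since transplant, or time since a matched switch date.

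**Working it through.** **The plan's own figure.** Section 7.3.6 gives about 10% first-year acute rejection on a cyclosporine-based regimen and a review threshold of twice that: 2 × 10% = 20%, or 4 of 20. This reproduces. The sample size of 20 (section 3.4) has no alpha, power or margin to reproduce.

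**Inputs**
- p = 0.10, rejection by 12 months from transplant (section 7.3.6).
- t = months from transplant to switch: spread evenly over 0-3 (section 7.2.1) or over 1-3 (section 1.2), or all at 3 as a bound.
- f = share of first-year rejection that falls in months 0-3, spread evenly within them. The documents do not give it; 0.3, 0.5 and 0.7 are **assumed**.

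**Formula.** By switch time t, a fraction c = f × t/3 of first-year rejections has occurred. With no drug effect, the 12-month rate among patients rejection-free at the switch is

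r(t) = p(1 − c) / (1 − pc),

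averaged over t. Example with f = 0.5 and t = 3: c = 0.5, so r = 0.05 / 0.95 = 5.26%.

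Gap in 20 = 20 × (0.10 − r). The post-switch relative risk that would read as equal rates is 0.10 / r.

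| Switch times | f | Controls | Belatacept, no drug effect | Gap in 20 | Relative risk that reads as parity |
|---|---|---|---|---|---|
| Even over 0-3 months | 0.3 / 0.5 / 0.7 | 10% | 8.62 / 7.67 / 6.69% | 0.28 / 0.47 / 0.66 | 1.16 / 1.30 / 1.49 |
| Even over 1-3 months | 0.3 / 0.5 / 0.7 | 10% | 8.16 / 6.89 / 5.58% | 0.37 / 0.62 / 0.88 | 1.23 / 1.45 / 1.79 |
| All at month 3 (bound) | 0.3 / 0.5 / 0.7 | 10% | 7.22 / 5.26 / 3.23% | 0.56 / 0.95 / 1.35 | 1.39 / 1.90 / 3.10 |

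**Scale against chance.** The exact 95% interval for 2 of 20 is 1.2 to 31.7%. At 10% in each group, the standard deviation of the difference in counts is √(2 × 20 × 0.1 × 0.9) = 1.9 events.

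**A repair that would overshoot.** Suppose exclusion 9 were applied to controls over the whole of months 0-3. Controls would then show 7.22 / 5.26 / 3.23%, against 8.62 / 7.67 / 6.69% for belatacept with switches over 0-3 months. That is a false excess of 0.28 / 0.48 / 0.69 events in 20 against belatacept. Control eligibility therefore has to stop at the index date.

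**Immune sampling.** Week 24 is 168 days, about 5.5 months. For belatacept subjects it falls 5.5-8.5 months after transplant (switch at 0-3 months) or 6.5-8.5 months (switch at 1-3 months). Nothing ties the control sample to the same window.

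**The case against.** The plan partly addresses comparability. Controls are called matched, matching is blinded, DSA is matched at enrolment (which implies some control baseline), and the immune comparison asks for a comparable time. Section 4.2 gives no time origin for rejection, and sections 2.1 and 3.1.3 compare with conventionally treated patients at the centre, who may be a wider group than the 20 controls. Rejection is only summarised, in an exploratory study, and is not in the primary lists of the synopsis or section 3.3. The early share of rejection is assumed. The relative risks apply one effect through month 12 post transplant, although the CNI is tapered over the first month and treatment beyond 6 months is optional.

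Much of this limits the size of the problem. The relative risks are illustrations, not estimates of a belatacept effect, and the gap is well inside chance variation. None of it supplies a control index date or requires controls to be rejection-free at one. The only origin stated for rejection is transplant, and section 4.2 also summarises belatacept adverse events since transplantation, which fits that reading. A wider comparator group would carry the same bias.

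**Conclusion.** The concern holds and should be fixed. As written, the plan builds rejection-free time before the switch into the belatacept group and does not require it of controls. By this mechanism alone, the belatacept rate is understated by about 0.3 to 0.9 events in 20, and by at most 1.4 if everyone switched at month 3. This rests on the plan's 10% and the assumed 30-70% early share; the gap shrinks towards zero for switches soon after transplant.

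The net direction across all selection differences cannot be fixed from the documents. For the immune endpoints the control time point is ambiguous, and no direction of bias is claimed. Each patient's own baseline-to-week-24 comparison is unaffected.

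**What to change.** In sections 3.1.3 and 4.1:

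1. Give each control an index date equal to the matched subject's days since transplant at Day 1.
2. Using only information up to that date, require the control to be a first-transplant recipient, to meet the immunologic, infection-related (including EBV) and mTOR-inhibitor exclusions of section 5.2, and to be alive with a functioning graft and no biopsy-proven rejection. Do not apply exclusion 9 to time after index.
3. Match on DSA at index.
4. For the between-group comparison, count rejection, graft loss, PTLD and death from Day 1 or index in both groups.
5. Use the stored control samples nearest to index +4, +12 and +24 weeks.
6. Record CNI toxicity, CMV serostatus, induction agent, and MMF and prednisone at index in controls, and report the balance.
7. State that the rejection and survival comparator is the 20 matched controls, or apply the same index rule to any wider group.

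The cost is new wording plus eligibility and date checks on an existing cohort, with no new visits. The control pool will shrink by an amount the documents do not let us state, so some pairs may need a wider age band. Some stored samples may miss the index-based weeks, and the cohort's records may not hold every criterion. Selection by CNI toxicity remains and should be reported as a limitation.
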